6.2.2. Study Period

Assessments and events will be classified according to the time of occurrence relative to the study intervention period.

Table 17 Study Period Definition

Study Intervention Period	Definition
Pre-GSK3965193/Placebo Period	Date < GSK3965193/Placebo Start Date
GSK3965193/Placebo Monotherapy Period	GSK3965193/Placebo Start Date ≤ Date < GSK3965193/Placebo Last Date
GSK3965193/Placebo Off treatment period	GSK3965193/Placebo last dose ≤ Date < GSK3965193/Placebo Last date + 14 days
GSK3965193/Placebo Follow-up	GSK3965193/Placebo Last date + 14 days ≤ Date if the participant doesn't take part in the optional bepirovirsen extension or GSK3965193 Off treatment period ≤ Date < Bepirovirsen Treatment Period Start date
Bepirovirsen Treatment Period	Bepirovirsen Treatment Start date ≤ Date ≤ Bepirovirsen End date
Bepirovirsen Treatment Follow-up	Date > Bepirovirsen Treatment End date

6.2.3. Study Day and Reference Dates

The safety reference date is the study intervention start date and will be used to calculate study day for safety measures.

The efficacy reference date is [the date of randomization OR the study intervention start date] and will be used to calculate study day for efficacy measures and baseline characteristics, as well as efficacy durations.

The study day is calculated as below:

- Assessment Date = Missing → Study Day = Missing
- Assessment Date < Reference Date → Study Day = Assessment Date – Ref Date
- Assessment Date ≥ Reference Date → Study Day = Assessment Date – Ref Date + 1

6.2.4. Assessment Window

Data summaries will utilize the nominal visit descriptions as outlined in the Part 3 schedules of activities. In cases of early discontinuation or withdrawal visits, data will be assigned to a target visit whenever possible, using the visit window guidelines specified in the table below. For all parameters, including safety and efficacy (PD parameters), if multiple assessments occur within the same window, scheduled visits will be prioritized over unscheduled visits. In instances where all assessments are from unscheduled visits, the latest assessment will be taken for safety parameters, while the assessment closest to the scheduled visit will be prioritized for efficacy assessments.

CCI

For data summaries by visit, baseline, scheduled visits with nominal visit description will be displayed. However, for determining the worst-case post baseline unscheduled visit assessments will be considered. In general, all un-scheduled visits will be displayed in the listing.

6.2.5. Multiple measurements at One Analysis Time Point

When triplicate ECG and/or Vital assessments are taken, mean of the measurement will be calculated first and summary statistics will be based on the calculated mean. This will be applied to both baseline and post baseline assessments.

For lab tests on a study day, if more than one assessment is taken on the same day, the test from a central lab will be taken over the test from a local lab. If multiple assessments are taken from the same type of lab, the worst case will be used.

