**7.1.5. Haematological Stopping Criteria (Part 3 Bepirovirsen Monotherapy and Part 4 only)**

[figure not shown]
During Part 3 bepirovirsen monotherapy and Part 4, if a participant develops signs or symptoms of thrombocytopenia, obtain a platelet count (local lab) as soon as possible and hold dosing until the platelet count is confirmed. If the platelet count is uninterpretable or below lower limit of normal (LLN) reference range, re-check the platelet counts as soon as possible. Samples showing platelet clumping should also be repeated.

Participants with platelet values **CCI** will undergo further assessment

[figure not shown]
including, but not necessarily limited to, anti-platelet antibodies. If the participant has a positive anti-platelet antibody, study treatment should be discontinued, including bepirovirsen, permanently. Monitor until platelet abnormalities resolve, stabilize, or return to within baseline values.

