### 9.4.1. General Considerations

Unless otherwise specified, baseline will be the last value/assessment before the first dose of study treatment (Day 1 pre-dose). If there are multiple assessments collected at the same scheduled time, the average of these assessments will be used as the baseline.

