4.1.3. Baseline Definition

Unless otherwise stated, if baseline data is missing, no derivation will be performed, and baseline will be set to missing.

Table 3 Baseline definition of different parameters for GSK3965193 Monotherapy

Parameters	Study Assessment Visit considered as Baseline for GSK3965193 monotherapy	Derivation of Baseline
12-Lead ECG	Pre-dose Day 1	Average of triplicate ECG measurements
Vital Sign	Pre-dose Day 1	Average of triplicate Vital Sign parameters measurement
Sensory nerve conduction test (SNCV)	Screening, Day -1	The best measurement out of Screening and Day -1 will be considered as baseline, where best being the higher measurement.
Nerve Function	Screening, Day -1	The worst measurement out of Screening and Day -1 will be considered as baseline, where worst being the higher total score.
Cognitive assessment	Day -1 or Prior to dosing Day 1 (whichever is latest)	Single measurement
Clinical laboratory (Chemistry and hematology)	Day -1 or Prior to dosing Day 1 (whichever is latest)	Single measurement
Liver Function	Day -1 or Prior to dosing Day 1 (whichever is latest)	Single measurement
Prothrombin time (PT), international normalized ratio	Day -1 or Prior to dosing Day 1 (whichever is latest)	Single measurement
Urinalysis	Day -1 or Prior to dosing Day 1 (whichever is latest)	Single measurement

Parameters	Study Assessment Visit considered as Baseline for GSK3965193 monotherapy	Derivation of Baseline
Urine albumin-creatinine ratio (ACR)	Day -1 or Prior to dosing Day 1 (whichever is latest)	Single measurement
HBsAg, HBV DNA	Prior to dosing Day 1	Single measurement
CCI	CCI	CCI

Table 4 Baseline definition of different parameters in optional Bepirovirsen monotherapy

Parameters	Study Assessment Visit considered as Baseline for Optional Bepirovirsen arm	Derivation of Baseline
Vital Sign	CCI	Single measurement
Clinical laboratory (Chemistry and hematology)		
Urinalysis	CCI	Single measurement
Urine albumin-creatinine ratio (ACR)		
HBsAg, HBV DNA		

Note: Unscheduled visits prior to dosing will also be considered while deriving baseline.

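### The Part 3 SAP's worst-of-same-day laboratory rule is not limited to post-baseline safety values, so a duplicated baseline is shifted in one direction where the protocol averages

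*SAP*

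**What the plan says.** **SAP (Part 3) 6.2.5** deals with several measurements at one time point. Triplicate ECGs and vital signs are averaged, and of this it says "This will be applied to both baseline and post baseline assessments". For laboratory tests on the same day, "the test from a central lab will be taken over the test from a local lab". After that, "If multiple assessments are taken from the same type of lab, the worst case will be used". The laboratory paragraph names no period, no group of analytes and no exception for unusable samples. It does not say which direction is worst for HBsAg or HBV DNA.

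**Protocol 9.4.1** sets the baseline: "Unless otherwise specified, baseline will be the last value/assessment before the first dose of study treatment (Day 1 pre-dose"). It adds: "If there are multiple assessments collected at the same scheduled time, the average of these assessments will be used as the baseline". It gives no averaging rule after baseline.

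**SAP 4.1.3, Table 3** plans one measurement for each laboratory baseline. Safety laboratory baselines are timed as "Day -1 or Prior to dosing Day 1 (whichever is latest"); HBsAg and HBV DNA are timed before dosing on Day 1. The note below Tables 3 and 4 says "Unscheduled visits prior to dosing will also be considered while deriving baseline". Neither the tables nor the note says what to do with two results on the same day.

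**SAP 6.2.4** prefers scheduled to unscheduled results within a window, for safety and PD parameters alike. If all are unscheduled, it takes the latest for safety and the one nearest the scheduled visit for efficacy.

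**SAP 4.8, Table 12** lists changes from the protocol to the bepirovirsen-arm endpoints, the analysis sets and the estimands. Baseline averaging is not listed.

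**Protocol 7.1.5**, for the Part 3 bepirovirsen phase and Part 4, says: "Samples showing platelet clumping should also be repeated".

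**The concern.** Choosing the worse of two valid results is directional. For post-baseline safety summaries that is a normal, conservative choice. At baseline it works the other way: the reference is pushed toward abnormal, and later worsening looks smaller in the change-from-baseline tables.

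For HBsAg the baseline enters every change value, and so the maximum reduction that is the primary PD variable (SAP 4.1.1). If worst is read as highest, an affected participant's reduction is overstated. The programmer has to guess the direction, although Table 3 does spell out what best and worst mean for nerve conduction and nerve function.

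The rule also does not separate a valid result from an unusable one. A clumped sample can give a falsely low platelet count. If that count is reported as a number, worst-case selection prefers it to the repeat.

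**Working it through.** The documents state no figure to reproduce. The check is a reading of the text plus a size calculation.

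**1. Does the rule reach baseline?** Nothing in 6.2.5 excludes it. The preceding paragraph of 6.2.5 names both periods for ECG and vital signs, and 6.2.4 says post-baseline expressly when it describes worst-case determination. The laboratory sentence carries no such limit. Same-day pre-dose duplicates are possible because unscheduled pre-dose samples count toward baseline.

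**2. Does it conflict with the protocol?** For two pre-dose results at the same scheduled time, the protocol takes the average and the SAP takes the worst. For pre-dose results at different times, the protocol default is the last one. Both protocol rules are non-directional. After baseline the protocol has no averaging rule, so there is no conflict there.

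**3. Size of the shift for two values.** Let X1 and X2 be independent normal results with within-person SD s.
- Larger value = average + |X1 − X2|/2.
- X1 − X2 has SD s√2, so E|X1 − X2| = s√2 × √(2/π) = 2s/√π.
- Expected shift = s/√π = 0.564s. A simulation of 1,000,000 pairs gave 0.565.
- With three values the shift is 3s/(2√π) = 0.846s. With averaging it is 0.

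**4. HBsAg.** The documents give no within-person SD, so a range is assumed. Worst is read as highest.

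| Assumed SD (log10) | Baseline shift, affected participant | Share of the 0.5 log10 responder threshold |
|---|---|---|
| 0.05 | 0.564 × 0.05 = 0.028 | 6% |
| 0.10 | 0.564 × 0.10 = 0.056 | 11% |
| 0.15 | 0.564 × 0.15 = 0.085 | 17% |

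If 5% to 20% of an arm had duplicates (assumed), the arm mean would move by between 0.05 × 0.028 = 0.001 and 0.20 × 0.085 = 0.017 log10.

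**5. A safety example.** For ALT with an assumed within-person CV of 10%, 20% or 30%, an affected baseline is 5.6%, 11.3% or 16.9% too high. A later rise is understated by the same amount.

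**6. Which outputs are exposed?** Blinded randomisation makes the expected shift similar in both arms, so it largely cancels in the difference. It does not cancel in the group means, in the posterior probability that mean maximum reduction passes a cutoff (SAP 4.2.2.4), in the proportion with a decline of at least 0.5 log10 (SAP 4.3.1.2.2), or in within-arm safety changes.

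**7. Platelets.** A clumped value is kept because of the worst-case rule only if three things hold: the laboratory reports a number, the repeat is on the same day, and the repeat comes from the same type of laboratory. Protocol 7.1.5 asks for a local count and a prompt re-check, so this is plausible. Two other rules can also keep the bad value: central over local in 6.2.5, and scheduled over unscheduled in 6.2.4.

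**The case against.** The strongest reply is that the two rules have different triggers. Protocol 9.4.1 speaks of results at one scheduled time, while SAP 6.2.5 speaks of extra results on one day. Table 3 plans a single measurement and, for safety tests, uses the latest. SAP 6.2.4 already sorts scheduled from unscheduled results, PD parameters included. HBsAg and HBV DNA are treated as treatment-sensitive, and results that could unblind are withheld from sites, so repeats prompted by a result are unlikely once dosing has begun. No hypothesis is tested.

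Much of this stands. It makes affected participants few, and it confines the rule for HBsAg to ties that 6.2.4 leaves open. It does not remove the conflict where pre-dose results share a scheduled time, and no text says whether 6.2.4 or 6.2.5 is applied first.

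Four stronger readings are tempting, and the documents do not support them:
- *Worst-case selection contradicts the protocol at every visit.* Protocol averaging is for baseline only.
- *The primary treatment difference is biased.* The expected shift is similar in both arms.
- *Thrombocytopenia AESI incidence is inflated.* The AESI display in SAP Table 10 counts reported adverse events. Section 6.2.5 selects laboratory values and cannot change that count.
- *One retained platelet artefact adds 5 to 7 percentage points* (1/19 to 1/15, from the cohort size implied by the 20%, 4-or-more trigger in SAP 1.1.3). That trigger describes the GSK3965193/placebo cohort. In Part 3 the clumping instruction applies to the opt-in bepirovirsen set, whose size is not given.

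**Conclusion.** The point holds in limited form. For duplicated pre-dose laboratory results, SAP 6.2.5 replaces the protocol's average with a directional choice, and Table 12 does not declare it. The expected shift in an affected participant is about 0.56 within-person SD for two values. For HBsAg that is roughly 0.03 to 0.08 log10, and it rests on the assumed SD range, on independent normal errors and on reading worst as highest. Safety baselines move toward abnormal, and later worsening is understated.

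The platelet risk is confined to the conditions in step 7. It touches the PCI, grading and change-from-baseline summaries, and no size can be put on it.

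Few participants should be affected. The sponsor should still correct it, because the rule is directional, can reach the primary PD variable, leaves a choice to the programmer and is cheap to repair.

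**What to change.** Amend SAP (Part 3) 6.2.5 as follows:

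1. Limit worst case to valid post-baseline safety laboratory results.
2. For baseline, average valid same-day pre-dose results in line with protocol 9.4.1, on the log10 scale for HBsAg. If the sponsor prefers another rule, declare it in Table 12.
3. State that selection under 6.2.4 comes first, and give one non-directional tie rule for post-baseline HBsAg and HBV DNA. The protocol does not prescribe which; a mean of log10 values is one option.
4. Leave results that the laboratory flags as invalid out of summaries when a valid repeat exists, and show them in listings.

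The cost is a few sentences and a small change to the derivation program. No new data are needed.

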6.2.6. Handling of Partial Dates

Element	Reporting Detail								
General	
 Partial dates will be displayed as captured in participant listing displays. However, where necessary, display macros may impute dates as temporary variables for sorting data in listings only. In addition, partial dates may be imputed for 'slotting' data to study phases or for specific analysis purposes as outlined below. Imputed partial dates will not be used to derive study day, time to onset or duration (e.g., time to onset or duration of adverse events), or elapsed time variables (e.g., time since diagnosis). In addition, imputed dates are not used for deriving the last contact date in overall survival analysis dataset. 								
Adverse Events	
 Partial dates for AE recorded in the CRF will be imputed using the following conventions: 
 
 Missing start day	 
If study intervention start date is missing (i.e. participant did not start study intervention), then set start date = 1st of month.
 
Else if study intervention start date is not missing:
 
 If month and year of start date = month and year of study intervention start date, then 
 If stop date contains a full date and stop date is earlier than study intervention start date, then set start date= 1st of month. Else set start date = study intervention start date. 
Else set start date = 1st of month.
 	
 
 Missing start day and month	 
If study intervention start date is missing (i.e. participant did not start study intervention), then set start date = January 1.
 
Else if study intervention start date is not missing:
 
 If year of start date = year of study intervention start date, then 
 If stop date contains a full date and stop date is earlier than study intervention start date, then set start date = January 1. Else set start date = study intervention start date. 
Else set start date = January 1.
 	
 
 Missing end day	A '28/29/30/31' will be used for the day (dependent on the month and year).	
 
 Missing end day and month	No Imputation	
 
 	Missing start day	
If study intervention start date is missing (i.e. participant did not start study intervention), then set start date = 1st of month.
 
Else if study intervention start date is not missing:
 
 If month and year of start date = month and year of study intervention start date, then 
 If stop date contains a full date and stop date is earlier than study intervention start date, then set start date= 1st of month. Else set start date = study intervention start date. 
Else set start date = 1st of month.
	Missing start day and month	
If study intervention start date is missing (i.e. participant did not start study intervention), then set start date = January 1.
 
Else if study intervention start date is not missing:
 
 If year of start date = year of study intervention start date, then 
 If stop date contains a full date and stop date is earlier than study intervention start date, then set start date = January 1. Else set start date = study intervention start date. 
Else set start date = January 1.
	Missing end day	A '28/29/30/31' will be used for the day (dependent on the month and year).	Missing end day and month	No Imputation
Missing start day	
If study intervention start date is missing (i.e. participant did not start study intervention), then set start date = 1st of month.
 
Else if study intervention start date is not missing:
 
 If month and year of start date = month and year of study intervention start date, then 
 If stop date contains a full date and stop date is earlier than study intervention start date, then set start date= 1st of month. Else set start date = study intervention start date. 
Else set start date = 1st of month.
								
Missing start day and month	
If study intervention start date is missing (i.e. participant did not start study intervention), then set start date = January 1.
 
Else if study intervention start date is not missing:
 
 If year of start date = year of study intervention start date, then 
 If stop date contains a full date and stop date is earlier than study intervention start date, then set start date = January 1. Else set start date = study intervention start date. 
Else set start date = January 1.
								
Missing end day	A '28/29/30/31' will be used for the day (dependent on the month and year).								
Missing end day and month	No Imputation								

Element	Reporting Detail	
	Completely missing start/end date	No imputation
Concomitant Medications/Medical History	
 Partial dates for any concomitant medications recorded in the CRF will be imputed using the following convention: 	
	Missing start day	
If study intervention start date is missing (i.e. participant did not start study intervention), then set start date = 1st of month.
 
Else if study intervention start date is not missing:
 
 If month and year of start date = month and year of study intervention start date, then 
 If stop date contains a full date and stop date is earlier than study intervention start date, then set start date= 1st of month. Else set start date = study intervention start date. 
Else set start date = 1st of month.

	Missing start day and month	
If study intervention start date is missing (i.e. participant did not start study intervention), then set start date = January 1.
 
Else if study intervention start date is not missing:
 
 If year of start date = year of study intervention start date, then 
 If stop date contains a full date and stop date is earlier than study intervention start date, then set start date = January 1. Else set start date = study. intervention start date. 
Else set start date = January 1.

	Missing end day	A '28/29/30/31' will be used for the day (dependent on the month and year).
	Missing end day and month	A '31' will be used for the day and 'Dec' will be used for the month.
	Completely missing start/end date	No imputation

6.2.7. List of Abbreviations

Abbreviation	Description
AE	Adverse Event
AESI	Adverse Event of Special Interest
API	Active Pharmaceutical Ingredient
ATC	Anatomical Therapeutic Chemical
AUC	Area under the concentration time curve
BID	Twice Daily
CI	Confidence Interval
CL	Clearance
C _{max}	Maximum observed concentration
CPMS	Clinical Pharmacology Modelling and Simulation
CS	Compound Symmetry
CSH	Heterogeneous Compound Symmetry
CV	Co-efficient of variation
C _τ	Trough Concentration
DAIDS	Division of AIDS
DEC	Dose Escalation Committee
ECG	Electrocardiogram
FTIH	First time in humans
GSK	GlaxoSmithKline
HBsAg	Hepatitis B Surface Antigen
HBV	Hepatitis B Virus
LLOQ	Lower Limit Of Quantification
LOD	Limit of Detection
MMSE	Modified Mini-Mental Status Exam
NCV	Nerve Conduction Velocity
NOAEL	No Observed Adverse Effect Level
NQ	Non- quantifiable
OBE	Optional Bepirovirsen Extension
OPS	Output and Programming Specification
PBMC	Peripheral blood mononuclear cells
PCI	Potential Clinical Importance
PD	Pharmacodynamics
PK	Pharmacokinetics
PLWCHB	Participants Living with Chronic Hepatitis B Infection
PT	Preferred Term
QTc	Electrocardiogram QT interval corrected for Heart Rate
RAPIDO DV	Reporting and Analysis Plan Improving Design and Delivery of Output Data Viewer
SAE	Serious Adverse Event
SAP	Statistical Analysis Plan
SD	Standard Deviation

Abbreviation	Description
SNCV	Sensory Nerve Conduction Velocity
SOC	System Organ Class
SRM	Study Reference Manual
$t_{1/2}$	Apparent terminal half-life
TCNS	Toronto Clinical Nerve Conduction Scoring System
T_{max}	Time to maximum observed concentration
WHO	World Health Organization
α	Alpha
β	Beta
λ_z	Lambda-z – Terminal Phase Rate

6.2.8. Trademarks

Trademarks of the GlaxoSmithKline Group of Companies
None

Trademarks not owned by the GlaxoSmithKline Group of Companies
NONMEM
SAS
WinNonlin

1. INTRODUCTION

[figure not shown]
The purpose of this Statistical Analysis Plan (SAP) is to describe the planned analyses for study Parts 1, 2A and 2B to be included in the Clinical Study Report for Protocol 214760. Analyses of Parts 3 and 4 will be covered in the separate SAP. All details of the dose escalation process and associated data review are outlined in the dose escalation plan. Metabolite evaluations will be conducted by DMPK and are not covered in this SAP.

Descriptive study population analyses such as summary of demography and baseline characteristics and additional detail with regards to data handling conventions and the specification of data displays will be provided in the Output and Programming Specification (OPS) document.

1.1. Objectives, Estimands and Endpoints

1.1.1. Objectives and Endpoints

Objectives	Endpoints
Part 1 and 2 (Healthy Participants)	
Primary	

 To assess the safety and tolerability of oral administration of GSK3965193 	
 Incidence of adverse events (AEs), serious adverse events (SAEs), withdrawals due to AEs Incidence of clinically significant laboratory parameters (haematology, clinical chemistry, urinalysis), vital signs, cardiac parameters (electrocardiogram [ECG]), and sensory nerve conduction (Part 2A)

 To evaluate the PK characteristics of single and repeat doses of GSK3965193 	
 Area under the plasma-concentration time curve (AUC): AUC(0-∞) for single dose and AUC(0-tau) for repeat dose. Maximum observed plasma drug concentration (C_{max}), time to maximum observed plasma drug concentration (T_{max}), and apparent terminal half-life (T_{1/2}) will be calculated as data permits per part

Objectives	Endpoints
Secondary	

To investigate the effect of food on the PK characteristics of single tablet doses of GSK3965193	
Area under the plasma-concentration time curve (AUC): AUC (0-∞), and maximum observed plasma drug concentration (C_{max}) as data permits
Exploratory	

CCI
 	

